### 5.1.2. Analysis of Adverse Events

Number and percentage of subjects with at least one particular AE (unsolicited/solicited) will be tabulated. Unsolicited AEs will be summarized by System Organ Class and Preferred Term. Solicited AEs will be summarized by class (local, systemic) and preferred term.

For solicited AEs following tables will be provided: summary, by worst severity grade, grade 3, related (systemic only), time to onset (in days) and duration (in days) for most frequent events and body temperature. Note: Duration is defined as number of days from the start of the event until resolution of the event. The time to first onset is defined as (date of first onset – reference date + 1). The reference date is the start date of the vaccination period.

For unsolicited AEs following tables will be provided: summary table (including SAE, fatal outcome, AESI and discontinuation), all events, most frequent, grade 3, permanent stop of vaccine, related, SAE and AESI.

Listings and/or subject narratives will be provided as appropriate, for those subjects who die, discontinue study vaccinations due to an AE, or experience a severe or serious AE.

### 5.1.3. Transforming On-site Assessments and Diaries of Solicited Adverse Events into an Analysis Format

Solicited events are always allocated to the respective Post Dose period.

When creating the analysis dataset for solicited AEs (dataset ADAESOL), solicited AEs (recorded by day) need to be converted into the format of unsolicited AEs (recorded by event). For this purpose, the start date of the AE will be considered as the date of first occurrence of the solicited AE (both local and systemic). If on subsequent day(s), the same grade is reported, the last reported date is used as the end date of the AE. A new record is created in case the grade of the event changes. If there is a time gap of at least 1 day between 2 (or more) occurrences of the particular solicited AE, then the second (and/or next) occurrence will be considered as a new AE. In case no data is reported for a day, this is analyzed as no event reported. If the on-site assessment differs in grade or relatedness with a corresponding day (eg, day of vaccination) of diary data, the on-site assessment should be recorded as a separate record in the database. The following example shows how the solicited AE should be converted into a format of unsolicited AEs:

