2. OBJECTIVES, ENDPOINTS, AND HYPOTHESIS

2.1. Objectives and Endpoints

Objectives		Endpoints		
Primary		_		
To assess safety/tolerability of the differe vaccine regimens	nt •	Solicited local and systemic adverse events (AEs) for 7 days after each vaccination.		
	•	AEs for 28 days after each vaccination.		
	•	Discontinuations from vaccination/from study due to AEs.		
	•	Serious adverse events (SAEs) and AEs of special interest (AESIs) of confirmed HIV infection during the course of the study, including the LTE phase.		

Objectives	Endpoints
• To assess Envelope (Env)-binding antibody (Ab) responses of the 2 different vaccine regimens.	Env-specific binding Abs (titers and breadth).
To assess safety/tolerability of a late boost vaccination.	Solicited local and systemic AEs for 7 days after the late boost vaccination.
	• AEs for 28 days after each the late boost vaccination.
	 SAEs and AESIs of confirmed HIV infection until the end of the study.
	AESIs of TTS for 6 months after the late boost vaccination
Secondary (applicable to main study, LTE and late	boost vaccination)
• To assess neutralizing Ab (nAb) responses,	• Env-specific nAbs (titers and breadth)
Ab functionality (as assessed by phagocytosis), and Ab isotyping.	• Env-specific functional Abs (phagocytosis score and breadth).
	• Env-specific binding Ab isotypes (immunoglobulin (Ig)A, IgG1-4) (titers and breadth).
To assess T-cell responses.	 Interferon gamma (IFNγ) peripheral blood mononuclear cell (PBMC) responders to mosaic and potential T-cell epitopes (PTE) peptide pools of Env/group-specific antigen (Gag)/polymerase (Pol).
	 Cluster of differentiation (CD)4+ and CD8+ T-cell functionality (% cells producing ia, IFNγ, interleukin 2 (IL-2), IL-4, tumor necrosis factor α [TNFα]).
	 T-cell development with emphasis on follicular helper T- cells and memory differentiation.^d
Exploratory (applicable to main study, LTE and lat	e boost vaccination)
• To explore whether the adenovirus serotype 26 (Ad26) vector is shed after vaccination.	 Polymerase chain reaction (PCR) positive for Ad26 sequences (urine and mid-turbinate swab).
To explore Ab functionality (other than phagocytosis).	• Ab functionality evaluation (such as Ab-dependent cellular cytotoxicity [ADCC], Ab-dependent complement deposition [ADCD]; excluding phagocytosis (ie, Ab-dependent cellular phagocytosis [ADCP]).
• To explore Ab Fc characterization.	• Ab Fc (sub)typing.

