After vaccination, subjects will remain under observation at the study site for at least 30 minutes for presence of any acute reactions and solicited events. In addition, subjects will record solicited events in a diary for 7 days post-vaccination. All subjects will be provided with a diary and instructions on how to complete the diary (Section 9.1.1). Diary information will be transcribed by the study personnel in the appropriate CRF pages. Once a solicited symptom from a diary is considered to be of severity Grade 1 or above, it will be referred to as a solicited adverse event. For AE severity criteria, see Section 12.1.3.

Injection Site (Local) AEs

Subjects will be asked to note in the diary occurrences of pain/tenderness, erythema and induration/swelling at the study vaccine injection site daily for 7 days post-vaccination (day of vaccination and the subsequent 7 days). The extent (largest diameter) of any erythema, and induration/swelling should be measured (using the ruler supplied) and recorded daily.

• Injection Site Pain/Tenderness

Injection site pain (eg, stinging, burning) is an unpleasant sensory and emotional experience associated with actual or potential tissue damage and occurring at the immunization site (with or without involvement of surrounding tissue). Injection site tenderness is a painful sensation localized at the injection site upon palpation and/or movement of the limb. Due to subjective nature of the reaction, the severity assessment of pain/tenderness is self-reported.¹²

• Injection Site Erythema

Injection site erythema is a redness of the skin caused by dilatation and congestion of the capillaries localized at the injection site. It can best be described by observation and measuring.

• Injection Site Swelling/Induration

Injection site swelling is a visible enlargement of an injected limb. It may be either soft (typically) or firm (less typical). Injection site induration is a palpable thickening, firmness, or hardening of soft tissue, usually has well-demarcated palpable borders, can be visible (raised or sunken compared to surrounding skin), is often 'woody' to touch and has a flat shape. As differentiation between swelling and induration may be difficult without health care professional's assessment, both symptoms have been combined to allow self-assessment by the subjects. Both swelling and induration can best be described by observation and measuring. ^{21,22}

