### 5. SAFETY

The safety and tolerability endpoints are:

- Unsolicited AEs 28 days following each vaccination
- Solicited local and systemic AEs (reactogenicity), collected daily from day of vaccination for 7 days post-vaccination (day of vaccination and the subsequent 7 days).

The safety and tolerability analysis will be performed on the FA set. Specifically, the analysis for solicited adverse events will be done on those subjects in the FA set for whom reactogenicity assessments are available in the database (either via on-site assessments or via the diary pages of the CRF).

Safety data will be tabulated per period by regimen. Only the active periods will be shown in the tables (AE, Lab, VS), except for SAEs. In addition, for a selection of tables (AE, Lab), tabulations per subject by vaccine and per dose by vaccine will be provided.

For the subject receiving the late boost vaccination, the AEs will be tabulated as follows:

- Reporting only the late boost period (post-dose 5) for the 2 LB regimens (LB Tetravalent Clade C-Mos and LB Placebo)
- Reporting all post doses (post-dose 1,2,3,4,5) for the vaccine they received (Any post-dose will not be included).

In the ‘per subject by vaccine’ analysis, the safety will be presented per periods (post-dose 1, 2, 3, 4) by vaccine rather than by regimen. A ‘post any dose’ period (= regimen phase in section 2.1) will be added, that summarizes the safety after all administered doses of a vaccine. The post-any-dose period allows determining how many subjects reported events after administration of a certain vaccine regardless the number of doses. Each subject is counted only once. In case a subject has the same event after more than one dose, it is counted only once (and in case of showing attributes, the worst corresponding attribute is shown) in the post-any dose period. The denominator is the number of subjects that received the considered vaccine in the considered period.

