### 5.1.1. Definitions

Solicited AEs shown in the tables are extracted from the diary pages of the CRF. For unsolicited AEs, only the AEs within the 28-day period following each vaccination will be presented in the safety tables except for SAE and AESI (AE of special interest), which will be captured and tabulated in the outputs covering the whole study period. All other collected unsolicited adverse events will be presented through listings.

Solicited local AEs will be by definition considered as related to the study vaccine.

The severity of the AEs will be classified as grade 1 to 4. Solicited events that are graded less than grade 1, are not considered as AE. In case no grades are available, the grading of the solicited events will occur according to the grading list in attachment 1 of the CTP.

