#### **5.1.4. Handling of Missing Data for Adverse Events**

Missing data will not be imputed. Subjects who do not report an event will be considered as subjects without an event. The analysis of the solicited AEs will include only documented safety data (i.e. in case severity is missing it is not considered an event).

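### A subject with no diary for a dose stays in the solicited-AE denominator for that dose as a non-reactor, so reported incidence of a primary safety endpoint is biased downward

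*SAP*

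**What the plan says.** Protocol 2.1 lists "Solicited local and systemic adverse events (AEs) for 7 days after each vaccination" among the primary endpoints and sets the same endpoint for the late boost. The SAP's rules for it are spread over several sections:

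- **Who is analysed (SAP 5):** "those subjects in the FA set for whom reactogenicity assessments are available in the database", where the data may come "either via on-site assessments or via the diary pages of the CRF". The on-site source is the post-dose observation in Protocol 9.3: "subjects will remain under observation at the study site for at least 30 minutes for presence of any acute reactions and solicited events".
- **Where events come from (SAP 5.1.1):** the tables draw solicited events from the diary pages.
- **Undocumented days (SAP 5.1.3):** "In case no data is reported for a day, this is analyzed as no event reported".
- **Undocumented subjects (SAP 5.1.4):** "Subjects who do not report an event will be considered as subjects without an event".
- **Missing grade:** SAP 5.1.4 says "in case severity is missing it is not considered an event". SAP 5.1.1 says that when no grade is available, "the grading of the solicited events will occur according to the grading list in attachment 1 of the CTP".
- **Denominators (SAP 5):** the by-vaccine tables use everyone who received the vaccine in the period. The per-dose tables use every dose administered. The SAP does not say whether the restriction to subjects with reactogenicity data overrides either of these.

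**The concern.** The entry rule and the counting rules do not fit together. A check of at least 30 minutes is enough to enter an analysis that covers the day of vaccination and the 7 days after it. The events themselves are read from a different source, the diary, and silence in the diary is scored as absence of a reaction. Because availability is judged per subject, diaries returned for other doses also keep a subject in a dose for which nothing was recorded.

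The protocol plans no formal testing of safety data, so the descriptive incidence rates are the safety result. A rule that lowers them systematically acts directly on what will be reported. The SAP specifies neither a table of diary completeness nor a sensitivity analysis, so a reader of the report could not tell how large the effect was.

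**Working it through.** **1. Two subjects followed through the rules**

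- Subject A receives a dose, has no symptom during the on-site observation and returns no diary. Section 5 admits the subject through the on-site assessment. The diary pages hold no events (5.1.1). Each undocumented day is no event (5.1.3), so the subject is event-free (5.1.4). Contribution: 0 to the numerator, 1 to the denominator.
- Subject B returns diaries for doses 1, 2 and 4 but has neither source for dose 3. The subject has reactogenicity data in the database, so the restriction as worded does not remove dose 3. Contribution at dose 3: again 0 and 1.

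A subject with no assessment after any dose is excluded by section 5. However, the on-site observation follows every vaccination, so that exclusion may remove few people.

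**2. The nearest figures in the plan**

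Neither document gives a diary-return rate or an expected solicited-AE rate. The closest figures are the zero-event bounds in Protocol 11.3: below 12% for n = 25 and below 3% for n = 100, at 95% confidence. They reproduce:

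- Exact bound, 1 − 0.05^(1/n): 11.3% for n = 25 and 2.95% for n = 100.
- Approximation, −ln(0.05)/n: 11.98% and 3.00%.

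These bounds treat every subject as documented. For solicited events with 22 and 90 documented subjects (about 10% without a diary), the exact bounds become 12.7% and 3.27%.

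**3. Whole diary missing for a dose**

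Let p be the true rate and m the share of the dose denominator with no diary. If those subjects have the same true risk, and events caught on site are ignored, the expected reported rate is p(1 − m). Both p and m are assumptions.

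| True rate | m = 2% | m = 5% | m = 10% |
|---|---|---|---|
| 70% | 68.6% | 66.5% | 63.0% |
| 30% | 29.4% | 28.5% | 27.0% |

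With equal m in two arms the ratio is unchanged but the absolute difference shrinks by the same factor. A true 70% against 30% (40 points) is reported as 63.0 − 27.0 = 36 points at m = 10%.

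**4. Isolated missing days**

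If days are missing independently with probability q, an event lasting L days is lost only when all L days are missing, with probability q^L. At q = 10% this is 10% for L = 1, 1% for L = 2 and 0.1% for L = 3.

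**5. Weight of one missed reactor**

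- Group 1: 1/25 = 4 points.
- Late boost at the target minimum of 48 subjects randomized 3:1, giving 36 active and 12 placebo: 1/36 = 2.8 points and 1/12 = 8.3 points.

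**6. Missing grade**

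In Protocol Attachment 1, temperature and reaction diameter can be graded from a recorded measurement. Headache, fatigue, myalgia and chills are graded by interference with activities, and injection-site pain by use of the limb. A grade for these can be derived later only if that detail was recorded. Their Grade 1 is no or minimal interference or limitation, so a reported symptom is at least Grade 1. SAP 5.1.1 and 5.1.4 therefore give different answers for the same record.

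**The case against.** The strongest reply is that the SAP already restricts the analysis. Section 5 limits it to subjects with reactogenicity data, and 5.1.4 limits solicited events to documented data. A reader might infer that every missing diary is counted as no event. That is not so, because a subject with no assessment from either source is out. The gap is confined to subjects admitted by an on-site check, or by data from another dose.

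Other stronger readings also fail:

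- **All the solicited-AE rules err downward.** Duration under 5.1.3 runs from first to last day across missing days, a gap can create an extra record, and a local event with no site link is attributed to both products. The downward direction holds for subject-level incidence only.
- **The quoted missing-day rule produces the p(1 − m) loss.** It does not by itself. That formula describes a wholly missing diary (step 3 against step 4). It also overstates the loss in post-any-dose rows, where another dose can supply the event.
- **The comparison between arms is biased.** That would need diary return to differ by arm. The documents give no evidence of this, and the study is double-blind with syringe overlays.
- **Ungraded symptoms are simply deleted.** SAP 5.1.1 provides for grading from Attachment 1. The defect is a conflict between two rules.

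The protocol also works to keep diaries complete, through subject training, staff review with carry-over to the next visit, and a 24–72 hour contact after main-study doses. This stands as a reason to expect m to be modest, but it is weaker for the late boost. That schedule lists no 24–72 hour contact, and 20 subjects attend Visit 22b 3 days after the dose, before the diary period ends, so review of the complete diary falls to the visit one month after the dose. Incomplete diaries there are plausible but not shown.

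**Conclusion.** The point holds in a limited form. Applied as written, the rules keep a subject with no diary for a dose in that dose's denominator as a non-reactor. For incidence of a primary safety endpoint, this can only lower the reported rate.

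The relative understatement is about m per dose, assuming equal true risk in subjects without a diary and ignoring events caught on site. SAP 5.1.3 does keep a discrepant on-site assessment as its own record, although 5.1.1 says the tables come from the diary. Because m is not in the documents, the bias cannot be sized; if diary return is nearly complete, it is negligible. The documents support neither a claim of distorted comparisons between arms nor a material loss from isolated missing days of events lasting two days or more.

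The change is still worth making because it is cheap and alters a reported result. The SAP introduction says outputs up to Week 72 will not be repeated, so the practical target is the late-boost tables.

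**What to change.** - For each dose, and at least for the late-boost tables, define the solicited-AE denominator as subjects with one or more documented diary days for that dose. State that this overrides the by-vaccine and per-dose denominators for solicited events.
- List subjects with only an on-site assessment for a dose separately, with any event seen on site.
- Tabulate diary completeness (none, partial, complete) by dose and arm.
- Reconcile SAP 5.1.1 with 5.1.4: grade from Attachment 1 where the recorded data allow it, and show reported symptoms that cannot be graded in a separate grade-missing row.

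The cost is a few lines of SAP text, minor programming and slightly smaller denominators. Estimates on the new denominator are free of this bias only if diary non-return is unrelated to reactions, which the completeness table would help a reader judge. Extending the change to the main study would mean rerunning completed outputs; a note on main-study diary completeness would be a lighter alternative.

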#### Data from the Subject Diary

Subject: 0001

Solicited systemic AE: Headache

Solicited AE	On-site Assessment	Diary Data							
	Day 1 01Jan16	Day 1 01Jan16	Day 2 02Jan16	Day 3 03Jan16	Day 4 04Jan16	Day 5 05Jan16	Day 6 06Jan16	Day 7 07Jan16	Day 8 08Jan16
Grade	2	1	1	0	3	3	1	0	0
Relatedness	Doubtful	Probable							
Serious		N							
Outcome		Recovered/Resolved							

The data should be converted and stored in the AE dataset as follows:

Subject No.	AE	Start Date	Stop Date	Severity	Relatedness	Serious	Outcome	AEID
0001	Headache	01JAN16	01JAN16	2	Doubtful			1
0001	Headache	01JAN16	02JAN16	1	Probable	N	Recovered/Resolved	1
0001	Headache	04JAN16	05JAN16	3	Probable	N	Recovered/Resolved	1
0001	Headache	06JAN16	06JAN16	1	Probable	N	Recovered/Resolved	1

If a solicited AE ends after Day 8:

- The stop date of the event is the “Date of last day of symptom” as recorded in the eCRF and the “maximum severity” after Day 8 as recorded in the CRF. A separate record is created for this, in case this severity deviates from the previous record.

**Note:** To complete the start and end-date based on diary data, the date will be calculated based on the actual day that the AE occurred relative to vaccination and not on the reported date. For example, if the vaccination is on 01-JAN-2016, and the AE starts on Day 3, the start date will be set to the 03-JAN-2016, independent of the reported actual date.

For the calculation of duration, the first and last day is used, irrespective of whether interruptions occurred in between by missing reporting days or Grade 0 events. In the above example, the 4 records contribute to the same AE, therefore AEID is set to the same value and the duration of the AE is set to 6 for all records.

Step 1: Allocation of events to the periods:

Adverse events in the SDTM database are allocated to periods based on their start date/time. If the start date/time of an event falls between (or on) the start and stop date/time of a period, the AE is attributed to that period (treatment-emergent principle).

- In case of partial start or stop dates (i.e. time and/or day and/or month and/or year missing), the events are allocated to the periods using the available partial information on start and end date; no imputation will be done. If, for instance, the AE start date only month and year are available, these data are compared to the month and year information of the periods. This rule may lead to multiplication of the event as a consequence of its assignment to multiple periods.

- In case of a completely missing end date, the date is imputed by the cut-off date of the analysis for subjects still ongoing in the study, and by the end date of the last period for subjects who discontinued or completed the trial.

Step 2: Combination of events:

Overlapping/consecutive events are defined as events of the same subject with the same preferred term which have at least 1 day overlap or for which the start date of an event is 1 day after the end date of the preceding event. Overlapping/consecutive events may be combined into one AE or not, according to the following rules:

1) If overlapping/consecutive events start in one of the following periods - Screening or post dose extension (i.e. non-active periods) - followed by an AE in - post-dose period (active period) - they are allocated to their respective periods and are considered as separate events.

2) In case overlapping/consecutive events start within a single period, they are considered as one and the same AE. The individual events which contribute to this AE are retained as individual records in the ADaM database but are assigned the same onset, period, and total duration. All related attributes to the AE/phase/period should also be consistent with the new event.

3) In case overlapping/consecutive events start in both an active period followed by a non active period, they are allocated to the active period only and are considered as one and the same AE. The individual events which contribute to this AE are retained as individual records in the ADaM database but are assigned the same onset, treatment period, and total duration. All related attributes to the AE/phase/period should also be consistent with the new event.

4) In case an active period is followed by another active period, and the overlapping/consecutive events start in both periods, they are allocated to their respective period and are considered as separate AEs. The same rule applies for 2 non-active periods.

Remarks:

1. Events can only be combined into one and the same AE if their start and stop dates are known.
2. In case the completely missing end date is imputed (for period allocation), this date is also considered as a complete date.
3. Time is not considered when determining overlap of events.

